3.2 Rationale for the trial

This trial aims to confirm the effect and to evaluate the safety of faster-acting insulin aspart with the use of CSII in adults with T1DM. In the European Medicines Agency (EMA) and FDA note for guidance on clinical investigation of medicinal products for the treatment of diabetes, HbA_{1c} is considered the most widely accepted measure of overall, long-term glucose control. Consequently, change from baseline in HbA_{1c} 16 weeks after randomisation will be included as the primary endpoint 16,17 .

The trial is intended to confirm that faster-acting insulin aspart, with a faster onset of action, is capable of demonstrating superior control of excessive postprandial glycaemic excursion during a standardised meal test and of demonstrating superiority of faster aspart in 1, 5-anhydroglucitol as another measure of PPG control, compared to NovoRapid[®].

The trial also aims to confirm superiority and investigate the differences in interstitial glucose (IG) of faster-acting insulin as compared to NovoRapid[®] based on data from continuous glucose monitoring (CGM) in adults with T1DM treated with CSII.

Further the trial is designed to confirm superiority of faster aspart in terms of overall glycaemic control measured as HbA_{1c} when compared to $NovoRapid^{®}$.

Protocol Trial ID: NN1218-3854 UTN: U1111-1118-2480 EudraCT no.: 2010-024054-11	CONFIDENTIAL	Date: Version: Status: Page:	04 February 2016 4.0 Final 23 of 149	Novo Nordisk
---------------------------------------------------------------------------------	--------------	---------------------------------------	-----------------------------------------------	--------------

The trial is a part of phase 3 clinical development program designed to meet the regulatory requirements for obtaining a CSII indication for faster-acting insulin aspart worldwide.

 Trial ID: NN1218-3854
 CONFIDENTIAL
 Version: 4.0

 UTN: U1111-1118-2480
 Status: Final

 EudraCT no.: 2010-024054-11
 Page: 24 of 149

4 Objectives and endpoints

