If any clinically significant abnormalities occur at screening (Visit 1) and for lipids at randomisation (Visit 6), then these must be recorded on the Concomitant Illness/Medical History form in the eCRF. Any clinically significant deterioration of a pre-existing condition as well as any new clinically significant signs or symptoms should be reported as an AE in accordance with section 12.

Laboratory equipment in the central laboratories may provide standard analyses not requested in the protocol but produced automatically in connection with the requested analyses according to specifications in the laboratory standard operating procedures. Such data will not be transferred to the trial database, but abnormal values will be reported to the Investigator. The Investigator must review all available laboratory results for concomitant illnesses and AEs and report these according to this protocol. The review of laboratory reports must be documented either on the front page of the documents and/or in the Subject's medical record.

Laboratory samples will be destroyed after analysis on an ongoing basis.

8.4.1 1,5-anhydroglucitol

Blood samples will be drawn to determine the level of 1,5-anhydroglucitol in order to evaluate postprandial glycaemic fluctuations. The analysis will be performed by the central laboratory. Sampling timings are indicated in the flow chart, please see section $\underline{2}$.

Protocol Date: 04 February 2016 Novo Nordisk
Trial ID: NN1218-3854 Version: 4.0

Status:

Page:

Final

72 of 149

UTN: U1111-1118-2480 EudraCT no.: 2010-024054-11

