Step 4 in the hierarchical testing procedure is to confirm superiority of change from baseline in 1,5-anhydroglucitol 16 weeks after randomisation with faster-acting insulin aspart compared to NovoRapid[®].

Protocol	Date:	04 February 2016	Novo Nordisk
Trial ID: NN1218-3854	Version:	4.0	

 Trial ID: NN1218-3854
 CONFIDENTIAL
 Version: 4.0

 UTN: U1111-1118-2480
 Status: Final

 EudraCT no.: 2010-024054-11
 Page: 116 of 149

The change from baseline in 1,5-anhydroglucitol will be analysed using a model similar to 1), but with baseline 1,5-anhydroglucitol as a covariate.

Superiority will be confirmed if the upper boundary of the two-sided 95% confidence interval of the mean treatment difference (faster-acting insulin aspart minus NovoRapid[®]) is below 0.

Change from baseline of time spent in low IG (≤3.9 mmol/L [70 mg/dL]) during CGM 16 weeks after randomisation (Step 5)

The time spent in low IG is defined for each Subject at each CGM period as the accumulated time in hours spent below or equal to 3.9 mmol/L [70 mg/dL] from the first valid sensor value divided by the actual duration of the profile. To report the endpoint in minutes per 24 hours the ratio is multiplied by 1440.

Step 5 of the hierarchical testing procedure is to confirm superiority of change from baseline of time spent in low IG (≤3.9 mmol/L [70 mg/dL]) during CGM 16 weeks after randomisation with fasteracting insulin aspart compared to NovoRapid[®].

The change from baseline of time spent in low IG (\leq 3.9 mmol/L [70 mg/dL]) will be analysed with a model similar to 1), but with the baseline value of time in hypoglycaemia as covariate.

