1.2 Scope of the statistical analysis plan

This statistical analysis plan (SAP) is based on the statistical considerations of NN1218-3854 as planned in the trial protocol *Efficacy and Safety of Continuous Subcutaneous Insulin Infusion of Faster-acting Insulin Aspart compared to NovoRapid[®] in Adults with Type 1 Diabetes*, version 4.0 (dated 04 February 2016). It contains a more detailed description for deriving and calculation of endpoints. Furthermore, it details changes to the statistical considerations presented in the protocol.

The changes to the statistical considerations proposed in this SAP and the reasons for the changes will be reported in the clinical trial report (CTR).

2 Statistical considerations

General considerations

In general, for endpoints evaluated as a change from baseline and/or where a baseline adjustment is made, baseline is defined as information collected at randomisation (Visit 6). In case a measurement is not available at randomisation, the most recent measurement prior to randomisation will be used as baseline.

Two observation periods are defined, “in-trial” and “on-treatment”, and it will be specified which period each analysis will use.

- **In-trial:** the observation period from date of randomisation and until last trial -related Subject-site contact. The in-trial observation period includes data collected after discontinuation of randomised treatment.
- **On-treatment:** the observation period from date of first dose of randomised NovoRapid[®]/fast-acting insulin aspart and no later than 7 days after the day of last dose of randomised NovoRapid[®]/fast-acting insulin aspart. The on-treatment observation period includes data collected up to and including 7 days after discontinuation of randomised treatment.

All efficacy endpoints will be summarised and analysed using the full analysis set (FAS), unless otherwise stated. Safety endpoints will be summarised using the safety analysis set and analysed using the FAS.

Presentation of results from a statistical analysis will include the estimated mean treatment effects (LSMeans) for change from baseline, if applicable. Estimated mean treatment differences (or ratios) will be presented together with two-sided 95% confidence interval (CI) for all endpoints analysed statistically.

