For endpoints measured over time, mean values will be plotted to explore the trajectory over time. For survival endpoints (e.g. drop-out pattern) Kaplan-Meier plots are presented for each treatment.

Data collected before randomisation (Visit 6) will only be summarised descriptively.

Subjects that prematurely discontinue from treatment or withdraw from trial will attend end of treatment visits called visit 22A and 22B. Data collected at these visits will be reallocated to the next scheduled visit where the given assessment is planned. As a general rule, all observed values from randomised subjects will be used in all statistical analyses, but in case two different values are associated to the same visit in time, the use of a given value will depend on the estimand of interest. For the primary estimand the reallocated on-treatment value will not be used and for the secondary estimand the reallocated on-treatment value will be used. The estimands will be defined in the next section.

Testing strategy and estimands

The primary objective, to confirm the effect of CSII treatment with fast-acting insulin aspart in terms of glycaemic control by comparing it to CSII treatment with NovoRapid[®], in adults with T1DM, will be assessed by the change from baseline in HbA_{1c} using a non-inferiority approach.

More specifically the upper limit of the 95% confidence interval for the difference between fast-acting insulin aspart and NovoRapid[®] should be compared to a non-inferiority margin of 0.4%. If it is below or equal to 0.4% non-inferiority will be considered established and effect demonstrated.

The trial also aims to compare CSII treatment with fast-acting insulin aspart to NovoRapid[®] for a number of confirmatory secondary endpoints. The family-wise type I error rate will be controlled in the strong sense using a hierarchical (fixed sequence) testing procedure for the primary estimand. This is based on a priority ordering of the null-hypotheses, and testing them in this order using the two-sided 95% confidence interval approach until an insignificant result appears. The effect is that rejection of a null hypothesis only will be considered for analyses where all previous null-hypotheses have been rejected in favour of fast-acting insulin aspart.

The steps in the hierarchical testing procedure are as follows:

Step 1 (Primary analysis): HbA_{1c} non-inferiority of fast-acting insulin aspart versus NovoRapid[®]

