2.1 Sample size calculation

The primary objective of the trial is to confirm the effect of CSII treatment with fast-acting insulin aspart in terms of glycaemic control by comparing it to CSII treatment with NovoRapid[®] in adults with T1DM, using a non-inferiority approach. The non-inferiority margin of 0.4% (absolute) was chosen as described in section 5.2.1 of the protocol. The statistical evaluation will be done as described in section [2.3](#).

The trial also aims to confirm superiority of CSII treatment with fast-acting insulin aspart for a number of secondary confirmatory endpoints using the hierarchical testing procedure as described in section [2](#) (General considerations).

The sample size is determined to ensure sufficient power for the first step and second step in the hierarchical testing procedure.

In previous exploratory trials where CSII treatment with faster aspart has been investigated, the completion rates have been high. Therefore it is expected that treatment discontinuation might be as low as 4% where trial discontinuation constitutes half of these.

The power for the non-inferiority step is based on a t-statistic under the assumption of a one-sided test of size 2.5 %. A mean treatment difference of -0.1% for the comparison between fast-acting insulin aspart and NovoRapid[®] is expected. As trials in this population where Subjects are using insulin pumps and where data from treatment withdrawn subjects is retrieved are limited, a conservative estimate of the standard deviation (SD) in change from baseline in HbA_{1c} of 0.8% was chosen.

For determination of power in the second step in the hierarchical testing, where change from baseline in 1-hour PPG increment 16 weeks after randomisation is compared between fast-acting insulin aspart and NovoRapid® a t-statistic with a two-sided test of size 5.0% is used, where the treatment difference is expected to be at least 0.9 mmol/L [16 mg/dL]. The SD=3.4 mmol/L [62 mg/dL] in change from baseline in 1-hour PPG increments 16 weeks after randomisation based on laboratory analysed plasma glucose (PG) in a standardised meal test is considered reasonable, based on prior trials.

The power calculation is done using proc power in SAS Version 9.4. Please refer to [Table 2-1](#) for assumption of the sample size calculation.

Table 2-1 Specifications assumed for sample size calculation

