2.4 Secondary endpoints

2.4.1 Confirmatory secondary endpoints

If the effect of CSII treatment with fast-acting insulin aspart can be confirmed in the primary analysis, the trial also aims to confirm the superiority of CSII treatment with fast-acting insulin aspart, for a number of secondary confirmatory endpoints.

The steps used in the hierarchical testing procedure are as follows:

Step 1 (Primary analysis): HbA_{1c} non-inferiority of fast-acting insulin aspart versus NovoRapid[®]

Step 2: 1-hour PPG increment (meal test) superiority of fast-acting insulin aspart versus NovoRapid[®]

Step 3: HbA_{1c} superiority of fast-acting insulin aspart versus NovoRapid[®]

Step 4: 1,5-anhydroglucitol superiority of fast-acting insulin aspart versus NovoRapid[®]

Step 5: time spent in low IG (≤ 3.9 mmol/L [70 mg/dL]) superiority of fast-acting insulin aspart versus NovoRapid[®]

The primary estimand for the primary endpoint will be repeated for the confirmatory secondary endpoints, change from baseline in 1-hour PPG increment (meal test), change from baseline in 1,5-anhydroglucitol and change from baseline of time spent in low IG (≤ 3.9 mmol/L [70 mg/dL]) during CGM 16 weeks after randomisation. The analyses related to these estimands are defined below and will be used for the decisions to continue or not, throughout the hierarchical testing procedure. These analyses will be based on the FAS and use the in-trial observation period.

The secondary analysis 4) will also be repeated for the confirmatory secondary endpoints. The analysis will be based on the FAS and using the on-treatment observation period.

Change from baseline in 1-hour PPG increment 16 weeks after randomisation (meal test) (Step 2)

As the second step of the hierarchical testing procedure, change from baseline in 1-hour PPG increment 16 weeks after randomisation will be tested for superiority of fast-acting insulin aspart compared to Novo Rapid[®].

The 1-hour PPG increment will be analysed based on the laboratory measured values in the meal test, and is derived as the 1-hour PPG measurement minus the pre-prandial PG.

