Step 4 in the hierarchical testing procedure is to confirm superiority of change from baseline in 1,5-anhydroglucitol 16 weeks after randomisation with fast-acting insulin aspart compared to NovoRapid[®].

The change from baseline in 1,5-anhydroglucitol will be analysed using a model similar to 1), but with baseline 1,5-anhydroglucitol as a covariate.

Superiority will be confirmed if the upper boundary of the two-sided 95% confidence interval of the mean treatment difference (fast-acting insulin aspart minus NovoRapid[®]) is below 0.

Change from baseline of time spent in low IG (≤ 3.9 mmol/L [70 mg/dL]) during CGM 16 weeks after randomisation (Step 5)

The time spent in low IG is defined for each Subject at each CGM period as the accumulated time in hours spent below or equal to 3.9 mmol/L [70 mg/dL] from the first valid sensor value divided by the actual duration of the profile. To report the endpoint in minutes per 24 hours the ratio is multiplied by 1440.

Step 5 of the hierarchical testing procedure is to confirm superiority of change from baseline of time spent in low IG (≤ 3.9 mmol/L [70 mg/dL]) during CGM 16 weeks after randomisation with fast-acting insulin aspart compared to NovoRapid[®].

The change from baseline of time spent in low IG (≤ 3.9 mmol/L [70 mg/dL]) will be analysed with a model similar to 1), but with the corresponding baseline value as covariate.

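### If higher 1,5-anhydroglucitol is favourable, the Step 4 superiority rule points the wrong way: a true benefit almost always fails Step 4 and closes Step 5

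*SAP*

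**What the plan says.** SAP 2.4.1, under Step 4, confirms superiority if "the upper boundary of the two-sided 95% confidence interval of the mean treatment difference (fast-acting insulin aspart minus NovoRapid[®]) is below 0". Protocol 17.4.1 has the same criterion with the same sign: "mean treatment difference (faster-acting insulin aspart minus NovoRapid[®]) is below 0". In both documents Step 3 (HbA1c) also requires the upper limit to be below zero, and so does Step 2 (1-hour PPG increment).

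The analyses in SAP 2.4.1 are the operative gate; they "will be used for the decisions to continue or not, throughout the hierarchical testing procedure". SAP section 2 (Testing strategy and estimands) stops testing at the first non-significant step and adds that "rejection of a null hypothesis only will be considered for analyses where all previous null-hypotheses have been rejected in favour of fast-acting insulin aspart".

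On the marker itself, protocol 8.4.1 says only that it is sampled "to evaluate postprandial glycaemic fluctuations", and protocol 3.2 speaks of "demonstrating superiority of faster aspart in 1, 5-anhydroglucitol as another measure of PPG control". Neither place says whether a high or a low value is good. SAP section 3, which lists the departures from the protocol, does not mention the Step 4 rule.

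**The concern.** Premise, not found in the documents: 1,5-AG falls when glucose is high, so a higher value indicates better postprandial control. A benefit of faster aspart would then appear as a positive difference, test minus comparator. The Step 4 sentence looks like the HbA1c sentence carried over without reversing the sign, so it confirms superiority only when 1,5-AG is significantly lower on faster aspart.

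Step 4 is an alpha-controlled claim on a named secondary objective, and it is the gate to Step 5. If Steps 1 to 3 succeed and 1,5-AG improves, the written rule denies the claim and ends the sequence. In the opposite case, a significantly worse 1,5-AG would meet the written criterion for superiority, although such a result is discordant and less likely once PPG and HbA1c superiority have been shown. If the text stays as it is, someone must choose after unblinding between the explicit limit and the general requirement that nulls be rejected in favour of faster aspart.

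**Working it through.** **Inputs (SAP 2.1).** 225 per arm. 1-hour PPG increment: difference 0.9 mmol/L, SD 3.4. HbA1c: "A mean treatment difference of -0.1% for the comparison between fast-acting insulin aspart and NovoRapid[®] is expected", SD 0.8, margin 0.4. The plan gives no effect or SD for 1,5-AG, so I use an assumed range of standardised true differences, d = (faster aspart minus NovoRapid)/SD, of +0.1, +0.2 and +0.265. The last equals the plan's standardised PPG effect, 0.9/3.4.

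**Method.** Two-sample t-test, 448 degrees of freedom, critical value 1.965, noncentrality = d × √(225/2) = 10.607 × d. Covariate adjustment and imputation are ignored.

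**The plan's own figures.** Step 2: d = 0.9/3.4 gives 80.0% power, as stated. All nine Step 2 entries of the SAP's power table reproduce to within 0.1 percentage point. Step 1: distance to the margin 0.4 + 0.1 = 0.5, SD 0.8, gives more than 99.9%, as stated.

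**How often Step 4 is reached.** Step 3 with d = 0.1/0.8 = 0.125 has power 26.2%. Step 1 holds automatically when Step 3 passes. If Steps 2 and 3 are independent, both pass with probability 0.800 × 0.262 = 0.210. With an assumed correlation of 0.3 the figure is 0.236, and at SD 0.8 it cannot exceed Step 3's own 0.262. If the HbA1c SD were 0.6, Step 3 power would be 42.2% and the independent figure 0.800 × 0.422 = 0.338.

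**Step 4 under the two rules (225 per arm).**

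| True d | Noncentrality | Written rule: P(upper limit < 0) | Mirror rule: P(lower limit > 0) |
|---|---|---|---|
| +0.1 | 1.06 | 0.13% | 18.4% |
| +0.2 | 2.12 | 0.002% | 56.2% |
| +0.265 | 2.81 | 0.0001% | 80% |

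At d = 0 each rule passes 2.5% of the time, so for any positive d the written rule passes less often than that. In the other direction, a true d of −0.265 would meet the written rule about 80% of the time, taken marginally.

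**Whole path, steps independent.** Mirror rule: 0.210 × 0.184 = 3.9%, 0.210 × 0.562 = 11.8%, 0.210 × 0.80 = 16.8%. Written rule at d = +0.1: 0.210 × 0.00127 = 0.027%, and lower for larger d.

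**Dependence between steps.** This was simulated with 4 million draws per setting and a correlation of 0.3 between the PPG and HbA1c estimates. For correlations of −0.8 to 0 between the 1,5-AG and HbA1c estimates (the sign the premise implies), the written rule passes, given Steps 1 to 3, at most 0.13% of the time at d = +0.1. Even at +0.5 it passes 0.45%. At −0.3 the mirror rule passes 29.9% and 71.7% for d = +0.1 and +0.2, which gives whole-path figures of 0.236 × 0.299 = 7.1% and 0.236 × 0.717 = 16.9%. Independence therefore understates what the written rule forfeits.

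**The case against.** The strongest objection is that the favourable direction is nowhere in the documents. If lower 1,5-AG were favourable, the written sign would be right. That stands as a condition on the finding: what the documents alone show is that a confirmatory endpoint has no stated favourable direction. But the direction is a basic property of the analyte, which the sponsor can confirm at once, and no effect size or cited study is needed.

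Second, the general wording in SAP section 2 requires rejection in favour of faster aspart. This helps in one direction: an unfavourable 1,5-AG result could not properly open Step 5. It does not rescue a true benefit, because the explicit limit under Step 4 would still say that superiority is not confirmed. The wording exposes the conflict without settling it.

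Third, the reach is limited. The plan powers only Steps 1 and 2, about 79% of trials would stop before Step 4 on the plan's figures if the steps are independent, and the primary claim is untouched. All of that is true. It limits how often the error takes effect, but it does not make the criterion correct, and the error takes effect in exactly the successful scenario that the hierarchy was written for.

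**Conclusion.** On the premise that higher 1,5-AG is favourable, the Step 4 rule is wrong as written in both documents and should be corrected before unblinding. Once Steps 1 to 3 pass, a true 1,5-AG benefit of 0.1 SD or more fails Step 4 in more than 99.8% of trials if the 1,5-AG and HbA1c estimates are uncorrelated or negatively correlated, and Step 5 closes with it. Over the whole path with independent steps, the chance of confirming Step 4 falls from about 4%, 12% and 17% under the mirror rule (d = +0.1, +0.2, +0.265) to under 0.03%. The path figures depend on the assumed 1,5-AG effects, the plan's HbA1c and PPG assumptions and the assumed dependence between steps. The direction of the error depends only on the premise. Step 1 and Steps 2 and 3 are not affected.

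**What to change.** Before database lock and unblinding, state in SAP 2.4.1 that a higher 1,5-AG is favourable, and change the Step 4 criterion so that superiority is confirmed when the lower limit of the two-sided 95% confidence interval for faster aspart minus NovoRapid lies above 0. Enter this in SAP section 3 as a change from the protocol. The SAP is the stated place for it, since "it details changes to the statistical considerations presented in the protocol", and protocol section 17 has it finalised before database lock.

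The same sentence in protocol 17.4.1 should be aligned if the protocol is amended; otherwise the section 3 entry must make clear that the SAP rule supersedes it. While the text is open, write the decision limit for Step 5 as well, because neither document gives one.

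The cost is one sentence and one log entry, plus one sentence for Step 5. No patients and no extra data are needed. If the protocol text is also amended, approval or a favourable opinion from the IRB/IEC is needed first (protocol section 25).
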